6.0 BIOSTATISTICAL ANALYSIS

6.1 Quantitative

Given our small planned enrollment of 3 patients, we will present our quantitative findings either as individual data points or with medians and interquartile ranges. We plan no formal statistical testing.

6.2 Qualitative

We will conduct qualitative interviews with the RHH clinical care team, patient, and caregivers daily during admission and post-discharge. Semi-structured interviews will be recorded,

transcribed, and then analyzed using NVivo qualitative analysis software. We will audio record interviews to a local microphone system and send them for transcription to a HIPAA-compliant transcription service. Qualitative data will be analyzed using descriptive content analysis, two researchers will code the data independently. Following initial descriptive coding, themes and recurrent patterns may be identified with any differences resolved by consensus.

7.0 RISKS AND DISCOMFORTS

Uncommon: Complications of surgical and non-surgical procedures

Standard hospital procedures carry small risks and discomforts. For example, venipuncture can be painful and can lead to thrombophlebitis, but this is uncommon and readily rectifiable.

Uncommon: Device complications/malfunctions

IV pumps, vital signs monitoring patches, and the other devices used during home hospital uncommonly have malfunctions.

Uncommon: Radiation risks

Patients can receive radiography while admitted to home hospital, much the same as when they are admitted in the hospital. We do not anticipate that home hospital will in any way change the prevailing risk of radiation.

Common (but unchanged from usual care): Drug side effects and toxicities

Drug side effects and toxicities do occur during inpatient medicine, despite following best practices and evidence based medicine. We do not anticipate that home hospital will in any way change the prevailing rate of drug side effects and toxicities compared to usual care. For example, acute kidney injury can occur in patients receiving antibiotics, even when correct dosing occurs. Home hospital is equipped to monitor and respond to the common drug side effects and toxicities much the same as the standard of care (monitoring, diagnostics, fluids, etc).

Common (but improved from usual care): Psychosocial risks

Admission to the hospital can be a psychosocially difficult event, particularly for a senior. We believe home hospital will alleviate these typical risks.

8.0 POTENTIAL BENEFITS

- Remain in their home despite acute illness
 - Eat their own culturally concordant food
 - Sleep in familiar surroundings
 - Maximize time and interactions with their family and friends
- Improved health outcomes (we anticipate these from previous literature)
 - Reduced length of stay
 - Reduced complications while admitted
 - Less delirium
 - Fewer falls
 - Fewer health care associated infections

- Decreases reduction in functional status
 - Improved patient experience
- Clinical improvements to the standard of care
 - Point of care blood diagnostics (results at the bedside in <5 minutes);
 - Minimally invasive continuous vital signs, telemetry, and activity tracking, including clinical deterioration algorithms, steps taken, and sleep quality;
 - On-demand 24/7 clinician virtual video visits;
 - Ambulatory/portable infusion pumps that can be worn on the hip;
- Improved transitions of care
 - Ability to coach patients on their post-discharge care plan in the appropriate environment, with caregivers available, and with adequate time for teaching given provider to patient ratio

Potential benefits to society

- New evidence-based care paradigm for acute care hospitalization.
- Lower total medical expenditure. Allows for redirection of resources to areas in need.
- Might eventually lead to reduction in total hospitals in the U.S.

9.0 MONITORING AND QUALITY ASSURANCE

Independent monitoring of source data

The study's research assistant will collect all data denoted above. The PI will monitor the source data throughout the project.

Safety monitoring

If any of the following concerning safety events occur, a blinded monitoring committee will review the event to determine attribution to the intervention: fall, medication error, DVT/PE, mortality during admission, transfer back to hospital (committee cannot be blinded for this endpoint). If any of these events are felt to be due to the RHH intervention, they will be reported to the IRB with recommendations for appropriate actions to be taken. Decisions to modify the protocol or suspend the study will be made jointly by the study investigators, monitoring committee, and the IRB.

Outcomes monitoring

The MD and RN/paramedics will daily review quality and safety data as part of a rapid logistics improvement process.

Weekly, the MD and RN/paramedic will huddle to review quality and safety data as part of a rapid logistics improvement process.

Adverse event reporting guidelines

All adverse events denoted above under safety monitoring will be reported to the monitoring committee.

10.0 APENDIX

Rural definition and Ultra- rural definition:

Rural:

- Centers for Medicare & Medicaid Services (CMS) ambulance fee schedule: EMS super rural
- Rural-Urban Commuting Area Codes (RUCA) 4-10
- Frontier and Remote Area Codes (FAR) less than or equal to 4

Ultra-rural:

- Centers for Medicare & Medicaid Services (CMS) ambulance fee schedule: EMS super rural
- Rural-Urban Commuting Area Codes (RUCA) 10
- Frontier and Remote Area Codes (FAR) 4

Adverse events

- Fall
- Delirium
- Potentially preventable VTE
- New pressure ulcer
- Thrombophlebitis at peripheral IV site

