1.1.2 Rationale

About 1 in 5 Americans live in rural areas, totaling nearly 60 million people.⁸ Living in a rural area is associated with higher mortality⁹ and poor access to health care, with 23% reporting an average 34-minute drive to their nearest hospital.¹⁰ An acute illness that traditionally requires hospitalization represents a common critical moment in nearly every person’s life. While some in rural areas face intense travel burdens to obtain acute care, others simply go without. Even those who receive care in a hospital may encounter an environment that is unsafe, of poor quality or experience, and expensive.¹¹ This may be particularly true of rural hospitals.^{12,13} In response to this unacceptable geographic disparity, over the last year, our team has designed and refined the rural home hospital (RHH) model through background research, workflow mapping, prototyping, and rapid cycle testing. We conducted a simulation of RHH through a series of “mock admissions” with stable but chronically ill patients in rural Utah. We evaluated the processes, workflows, and technologies involved in RHH and collected qualitative data from the patients, caregivers, and RHH clinical team.

Building on the success of these detailed planning exercises, we propose deploying RHH to care for acutely ill patients in rural and ultra-rural settings in Utah as a proof of concept. This study will evaluate the feasibility and acceptability of the RHH intervention with 3 patients and synthesize key learnings which will be used to refine the RHH model and inform an implementation strategy going forward. If the home hospital model can be successfully deployed in rural and ultra-rural settings, a paradigm shift in access to acute care will occur, providing this care model to rural patients and clinicians.

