2.0 SPECIFIC AIMS

2.1 Primary Aim

Assess the feasibility of home hospital care in rural and ultra-rural settings in the United States by deploying a home hospital team to care for acutely ill rural patients at home.

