3.0 SUBJECT SELECTION

3.1 Inclusion

Patient inclusion criteria:

Patient clinical inclusion criteria:

- ≥ 18 years old
- Any infectious process (e.g., pneumonia, diverticulitis, cellulitis, complicated urinary tract infection)
- Heart failure exacerbation
- Asthma and chronic obstructive pulmonary disease exacerbation
- Atrial fibrillation with rapid ventricular response
- Diabetes and its complications
- Venous thromboembolism
 - This includes a patient who requires therapeutic anticoagulation and concomitant monitoring (thus requiring inpatient status)
- Gout exacerbation
- Chronic kidney disease with volume overload
- Hypertensive urgency
- End of life / desires only medical management
 - Regarding a patient who desires only medical management, this includes a patient who requires acute care for symptom management but declines any surgical intervention. This may include a patient who is about to transition to hospice care, for example, but still has the functional capacity to meet our criteria below. Under these circumstances, we would make sure that various contingencies, including possible transition to hospice care or hospital readmission, are completely understood by patients and caregivers as applicable.

Patient social inclusion criteria:

- Lives in rural or ultra-rural area (see definitions in Appendix) that can be served by one of our RHH clinicians.
- Has capacity to consent to study
- Can identify a potential caregiver who agrees to stay with patient for first 24 hours of admission. Caregiver must be competent to call care team if a problem is evident to her/him. After 24 hours, this caregiver should be available for as-needed spot checks on the patient.
 - This criterion may be waived for highly competent patients at the patient and clinician's discretion.

Patient caregiver inclusion criteria: (not required for patient participation):

- Age \geq 18 years old
- Has capacity to consent to study
- Lives with or nearby to patient

Clinician inclusion criteria:

- Any member of the rural home hospital (RHH) clinical team (MD, RN, paramedic, NP) who will be participating in the screening and recruitment of patients for the rural home hospital intervention and/or providing care to rural patients that enroll in the intervention.

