4.0 SUBJECT ENROLLMENT

4.1 Screening and recruitment

Patients:

- Acutely ill patient is screened and recruited as above.
- If participant agrees, the RHH MD will further describe the program, answer initial questions, and further assess whether the participant meets inclusion/exclusion non-clinical (e.g., social) and clinical criteria (please see the subject eligibility checklist)

Clinicians

- Members of the rural home hospital clinical team (MD, RN, paramedic, NP) that have expressed interest in participating in research activities and meet inclusion criteria will be approached by a member of the study team.

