4.4 Treatment Assignment

All eligible and agreeable patients will be enrolled in RHH.

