5.5 Data to be collected and when the data will be collected

5.5.1 Primary endpoint

Outcome measure	Data sources	Day(s) Obtained
RHH admission, daily care, and discharge processes accomplished	Process checklist (attachment) and semi-structured interviews with clinicians	Daily

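### With ultra-rural settings named in the primary aim, does the plan need a rule to secure, classify and report ultra-rural patients among its 3?

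*Combined protocol and SAP*

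**What the plan says.** Section 2.1 sets the aim: "Assess the feasibility of home hospital care in rural and ultra-rural settings in the United States". Section 1.1.2 describes the work in the same terms: "we propose deploying RHH to care for acutely ill patients in rural and ultra-rural settings in Utah as a proof of concept".

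The social inclusion criterion in section 3.1 accepts either class: "Lives in rural or ultra-rural area (see definitions in Appendix". Section 4.1 refers screeners to a checklist ("please see the subject eligibility checklist"), whose content is not in the file. Section 4.4 sets no quota or stratum: "All eligible and agreeable patients will be enrolled in RHH".

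The primary endpoint in section 5.5.1 is "RHH admission, daily care, and discharge processes accomplished", taken from a process checklist (also not in the file) and clinician interviews. It is not split by setting. Zip code is the only geographic item in section 5.5.3. Section 6.1 says: "Given our small planned enrollment of 3 patients, we will present our quantitative findings either as individual data points". Medians with interquartile ranges are the alternative, and formal testing is ruled out.

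The Appendix (section 10.0) defines each class by three schemes: the CMS ambulance fee schedule, RUCA codes and FAR codes. The first entry, "Centers for Medicare & Medicaid Services (CMS) ambulance fee schedule: EMS super rural", is the same under both headings.

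**The concern.** The aim joins two settings with *and*, while eligibility joins them with *or*. With 3 places and no reservation, the ultra-rural half of the aim could end with no data. Nothing in the endpoint, covariate or analysis sections plans to label a patient as ultra-rural, so a reader of the results might not be able to tell.

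The Appendix seems to add to the difficulty. It does not say whether any one criterion suffices or all three must hold, and one criterion is identical for both classes. Two screeners could read it differently, and the same address could be ultra-rural to one and ineligible to the other. At stake is what the feasibility conclusion may claim and, at the margin, who is eligible. No error rate or power is involved.

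**Working it through.** **Inputs.** Planned enrolment of 3 and no testing (section 6.1); either class eligible (3.1); all eligible and willing patients enrolled (4.4); zip code collected (5.5.3); class definitions from the Appendix. The plan gives no share of ultra-rural patients and no sample-size calculation, so there is no stated figure to reproduce.

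**Step 1: is the repeated line an error?** Set the two definitions side by side.

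| Scheme | Rural | Ultra-rural | Ultra-rural inside rural? |
|---|---|---|---|
| CMS ambulance schedule | super rural | super rural | yes, identical |
| RUCA | 4 to 10 | 10 | yes |
| FAR | 4 or below | 4 | yes |

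Every ultra-rural criterion lies within its rural counterpart. Under either reading, every ultra-rural address is therefore also rural, and the inclusion criterion reduces to being rural. A repeated line is what such nesting would produce. It may still be a slip, but the text does not show that it is.

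**Step 2: does the any/all reading matter?** Cross super rural (yes, no) with RUCA (below 4, 4 to 9, 10) and FAR (none, below 4, 4): 2 × 3 × 3 = 18 combinations.

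- *Any one suffices.* Only one combination fails every rural criterion (not super rural, RUCA below 4, no FAR code), so 18 − 1 = 17 are eligible. Ultra-rural: all 9 super rural combinations, plus 3 + 3 − 1 = 5 others with RUCA 10 or FAR 4, giving 14. Rural only: 17 − 14 = 3.
- *All must hold.* Eligible: 1 × 2 × 2 = 4. Ultra-rural: 1. Rural only: 4 − 1 = 3.

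Each reading sorts addresses cleanly into three groups, so once a reading is adopted nothing is ambiguous. The readings do differ: only 2 of the 18 combinations get the same label under both (one ultra-rural, one ineligible). The counts show that a reading has to be chosen. They do not measure impact, because the combinations are not weighted by population and some may not occur.

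**Step 3: how likely is a trial with no ultra-rural patient?** If a share p of eligible patients is ultra-rural and patients are independent, the chance of none among 3 is (1 − p)³. The plan gives no p, so take an assumed range:

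| p (assumed) | 0.05 | 0.10 | 0.20 | 0.30 | 0.50 | 0.70 |
|---|---|---|---|---|---|---|
| (1 − p)³ | 0.857 | 0.729 | 0.512 | 0.343 | 0.125 | 0.027 |

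The result runs from very likely to negligible, so the possibility is real but its size cannot be fixed from the documents.

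**Step 4: what would a reserved place buy?** It would guarantee one ultra-rural patient, if the place is filled. The price is an exception to section 4.4, slower enrolment, and possibly turning away an eligible and willing patient. The return could be as little as a single patient's experience of that setting.

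**Step 5: can the setting be shown without new text?** The area must be checked against the Appendix before a patient is admitted. Zip code is recorded at admission. With 3 patients, individual listing is already a planned presentation, and a patient's setting can stand beside that patient's process data.

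**The case for a change.** The best counter-argument is that a class derived afterwards needs a rule, and choosing the rule once the patients are known invites a convenient choice. The Appendix also decides eligibility, so the omission is more than cosmetic. Ultra-rural is named in the aim and separately defined, which suggests that the authors meant it to carry weight. A short clarification would cost little.

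Part of this stands. The any/all rule is not written down, and sections 5.5.1 to 5.5.3 and 6.1 list no class. But a screener cannot admit the first patient without adopting a reading, so a reading is in use before that patient's process data exist. The checklists cited in sections 4.1 and 5.5.1 may record it; they cannot be inspected here, so their silence cannot be assumed. A list of three separate classification schemes is naturally taken as alternatives, although the document's lists are mixed: the adverse events in the same Appendix are alternatives, while the social inclusion criteria apply together. With 3 patients, the report can give each one's codes and let the reader apply either reading, which leaves little room for a convenient choice.

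Naming both settings in the aim can describe the area of deployment and need not define two strata. The primary endpoint makes no claim by class.

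**Conclusion.** The observations are accurate, but no change to the plan follows. The unstated any/all rule and the unlisted class are missing detail that screening and a 3-patient listing would fill sensibly. The repeated line is consistent with nested definitions and is not shown to be an error. Reserving a place is a trade-off that a proof of concept of this size may fairly decline. Describing feasibility only for the settings actually enrolled is good reporting practice and does not depend on amending the plan.

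The consequence is confined to how widely a descriptive conclusion may be drawn from 3 patients: 0, 1, 2 or 3 of them may be ultra-rural, and no test, estimate or error rate depends on which. This rests on two assumptions: that screeners apply one reading consistently from the first patient, and that zip code or the screening records suffice to state each patient's setting.

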2.2 Secondary Aims

Asses RHH for its acceptability, experience, quality, and safety.

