5.5.2 Secondary endpoints

Outcome measure	Data sources	Day(s) Obtained
3-item Care Transition Measure	RA via patient	Within 1 week of discharge
Picker Experience Questionnaire	RA via patient	Within 1 week of discharge
Global satisfaction	RA via patient	Within 1 week of discharge
Perceived acceptability of RHH care	Post-discharge semi-structured interviews with clinicians, patients, and caregivers	Within 1 month of discharge
Perceived safety, quality of care, caregiver burden	Post-discharge semi-structured interviews with clinicians, patients, caregivers	Within 1 month of discharge
Escalation of care to hospital	RA via RN/EMTP	Daily
Adverse event*	RA via RN/EMTP	Daily
Unplanned mortality during admission	RA via RN/EMTP	Daily

Lab Orders, #	RA via RHH records	Daily
Length of stay	RA via RHH records	Discharge
Unplanned readmission(s) after index, # and y/n	RA via patient	30-days post-discharge
ED visit(s) after index, # and y/n	RA via patient	30-days post-discharge

*: see appendix

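### The adverse event endpoint is defined by a five-item list that names neither drug toxicity nor device malfunction, both given as risks in Section 7.0, so such an event managed at home can go uncounted and has no stated route to the committee

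*Combined protocol and SAP*

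**What the plan says.** Section 2.2 sets the secondary aim: "Asses RHH for its acceptability, experience, quality, and safety". Among the secondary endpoints in Section 5.5.2 is "Adverse event", obtained daily by the research assistant from the nurse or paramedic. The table gives no definition and its footnote refers to the Appendix.

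The Appendix (Section 10.0) gives five bullets: fall, delirium, "Potentially preventable VTE", "New pressure ulcer" and "Thrombophlebitis at peripheral IV site". No item for other events follows, and there is no general definition of an adverse event.

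Section 7.0 describes the risks of taking part. One heading is "Common (but unchanged from usual care): Drug side effects and toxicities", with kidney injury on correctly dosed antibiotics as its example. Another concerns devices: "IV pumps, vital signs monitoring patches, and the other devices used during home hospital uncommonly have malfunctions".

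Section 9.0 has its own five triggers for committee review: falls, DVT/PE, medication errors, deaths while admitted and transfers back to hospital. Its reporting rule sends to the committee only the events on that list.

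**The concern.** The protocol names harms it expects may occur, and then defines its adverse event endpoint by a list that leaves two of them out. A nurse or paramedic who completes the daily item has only the five Appendix terms to work from. A patient whose kidney function worsened on an antibiotic, or whose infusion was interrupted by a pump failure, could be entered as having had no adverse event if the problem was dealt with at home.

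At stake is the completeness of the safety account. Section 6.1 plans individual data points or medians and no testing, so the value of the safety data lies in recording what happened to each of 3 patients. Section 1.1.2 says the learnings will be used to refine the model and shape its implementation. Home-managed toxicities and failures of pumps or patches are learnings of that kind.

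**Working it through.** The documents give no event rate, power or threshold to reproduce. The check sets the lists side by side.

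**Step 1. Section 7.0 risks against the two lists.**

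| Section 7.0 risk | Appendix (5 events) | Section 9.0 (5 triggers) |
|---|---|---|
| Procedures (example: thrombophlebitis after venipuncture) | Yes, thrombophlebitis | No |
| Device malfunction | No | No |
| Radiation | No | No |
| Drug toxicity (example: kidney injury under correct dosing) | No | No; medication error is a different event |
| Psychosocial | No | No |

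The two lists share falls and VTE (with different wording for VTE), so together they cover 5 + 5 − 2 = 8 distinct event types. Neither drug toxicity nor device malfunction is among the 8. The radiation and psychosocial rows are not pursued: Section 7.0 expects no change in radiation risk and an improvement in psychosocial risk.

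**Step 2. What happens to particular events under the text as written.**

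| Event | Counted as adverse event (Appendix)? | Sent to committee (Section 9.0)? |
|---|---|---|
| Toxicity that shows as a fall | Yes | Yes |
| Toxicity that shows as delirium | Yes | No |
| Toxicity or malfunction that leads to transfer or death | Not as such; counted under the separate escalation or mortality endpoint | Yes |
| Pump failure that causes a wrong or missed dose | No | Plausibly, as a medication error |
| Kidney injury under correct dosing, managed at home | No | No |
| Malfunction that harms the patient or interrupts treatment or monitoring, with no listed event, medication error or transfer | No | No |

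The last two rows are the gap. No other quantitative row in Section 5.5.2 closes it: lab orders are counted by number, not by result, and length of stay gives no cause.

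**Step 3. Size.** Suppose one of the 3 patients has an event from the last two rows and no listed event, and the other two have none. The number of patients with an adverse event is then 1/3 if the event is counted and 0/3 under the present list. This is an illustration. The documents give no rate from which to say how likely it is.

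**The case against.** The strongest reply is that the study has other ways of seeing these events. Clinicians, patients and caregivers are interviewed daily during admission and again after discharge (Section 6.2). Daily progress notes are kept, and an alarm alerts the attending to delayed data transfer (Section 5.1). The primary endpoint rests on a daily process checklist (Section 5.5.1), an attachment that is not in the text reviewed and may well record device problems. Quality and safety data are reviewed daily and weekly (Section 9.0). All of this stands. A reader might infer that the study collects nothing on toxicity or malfunction, or that such events could never reach the committee, and the documents do not support either. What remains is that none of these routes is the adverse event endpoint, and none is stated to bring a home-managed event to the committee.

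It can also be said that the Appendix does not call its list exhaustive. That is true, and reading it as closed is an inference. But the endpoint has no other definition.

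Third, Section 7.0 expects drug toxicity to be unchanged from usual care. Drug toxicity is therefore a risk of taking part and not one specific to remote delivery; only the device risk is tied to the home technology. Nor would better recording test that expectation, because 3 patients without a comparator cannot estimate a difference in rates.

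Finally, a malfunction or data-transfer alarm with no effect on the patient is a process failure. Counting it as an adverse event would blur the endpoint. This stands, and it limits the fix.

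**Conclusion.** The point holds as a gap in how the safety endpoint is defined, and it should be closed before enrolment. Two risks the protocol itself names are absent from both the Appendix list and the Section 9.0 list. The gap is confined to events managed at home with no listed event, medication error, transfer or death. Its effect is on descriptive reporting in 3 patients; the primary feasibility aim is not affected.

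The conclusion assumes that the Appendix list is applied as written and that no unseen form adds to it. If the process checklist already records device problems, the device half of the gap shrinks to how those problems are classed and reported.

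A reader might also take the absence of infection from both lists as a contradiction, since Section 8.0 lists "Fewer health care associated infections" among the benefits. It appears there only as a benefit anticipated from earlier literature, not as a named risk or an aim of this study, so its absence is not an error.

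**What to change.** Add two items to the Appendix list, and so to the daily item in Section 5.5.2:

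- drug side effect or toxicity, including acute kidney injury, with a recording criterion chosen by the investigators;
- device malfunction (infusion pump, monitoring patch, point-of-care meter) that harmed the patient or interrupted treatment or monitoring.

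Add both to the Section 9.0 list, so that the reporting rule covers them. Record harmless malfunctions and data-transfer alarms separately, as process outcomes under the feasibility endpoint. Health care associated infection is an optional further item.

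The cost is two lines on an item already completed daily, and a few more entries and committee reviews for 3 patients. The adverse event count may look less favourable. No treatment or visit changes. The gain is a complete descriptive safety record.
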